3.2 Secondary Objectives

- 3.2.1** Compare different breast densities (entirely fatty, scattered fibroglandular densities, heterogeneously dense, extremely dense) and their impact on clip migration in both groups (retracted vs nonretracted).
- 3.2.2** Compare different approaches (lateral, medial, superior) to biopsy and evaluate if they have an impact on clip migration in both groups (retracted vs nonretracted).
- 3.2.3** Evaluate if thinner or thicker breasts result in more or less clip migration in both groups (retracted vs nonretracted).
- 3.2.4** Evaluate if patient's age correlates with more or less clip migration in both groups (retracted vs nonretracted).

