12.1 Sample size justification

A total of 250 female patients presenting to UAB for stereotactic biopsy will be randomly assigned as 1:1 ratio to Arm1 (n=125) with advancing the clip to the biopsy site and deploying, or Arm2 (n=125) with advancing the clip to the biopsy site and retracting 5 mm and then deploying. Our hypothesis is that retracting to clip 5 mm before clip deployment will decrease clip migration, e.g. only 20% or less of breast biopsy patients who will have significant migration (greater than 10 mm from the biopsy site) while advancing the clip to the biopsy site and deploying without retracting will have at least of 50% significant migration. This size of 125 in each arm will have 99.9% power to test 30% difference (20% vs 50%) or >90% power to test at least 20% difference in proportion of patients who will have significant migration using one-sided Fisher's Exact test at 5% significant level (Table 1).

Table 1 Statistical Power to Test Differences Between Two arms.

Significant migration in Arm1 (%)	Significant migration in Arm2 (%)	Type I error (%)	Power (%)
50	15	5	100
50	20	5	99.9
50	25	5	99.1
50	30	5	93.1
50	15	1	100
50	20	1	99.6
50	25	1	95.4
50	30	1	78.5

A sample size of 125 will also produce two-sided 95% confidence interval to estimate the mean distance of migration with 0.177 standard deviation to the limits for each arm. Patients enrollment is expected to be completed within one year.

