13.2 Statistical analysis plan

The primary objective of the number and percentage of breast biopsy patients whose clip has greater than 10 mm from the biopsy site as significant clip migration will be estimated and two-sided 95% confidence interval will be calculated using the method of Clopper–Pearson interval for each arm separately. Fisher exact test will be used to examine if there is significant association between arms in proportion of significant clip migration. The average of distance of clip migration will be estimated with two-sided 95% CI for each arm separately using normal approximation. Two-group student t-test will be used to evaluate the mean difference in the distance of migration from the original biopsy site between arms.

Correlation between migration and breast densities (entirely fatty, scattered fibroglandular densities, heterogeneously dense, extremely dense), different approaches (lateral, medial, superior) to biopsy, if thinner or thicker breasts and age under procedure of retracted (arm2) vs nonretracted (arm1) will be evaluated in two ways for the secondary objectives. First, we will consider significant clip migration (yes, no) as binary outcome. Analysis of Variance method (ANOVA) will be used to compare age differences with controlling of procedures, and Cochran -Mantel-Haenszel Test will be

used to compare differences in categorical variables, e.g. breast density stratified by retracted (arm2) vs nonretracted (arm1). Logistic regression analysis will be explored to identify significant factors associated with clip migration. Odds ratio and two-sided 95% CI will be presented for each factor significantly contributed in the model. Second, we will consider distance of clip migration (mm) as continuous outcome. ANOVA will be used to evaluate the strength of association (beta coefficient in the regression model) and identify significant of factors associated with the distances of migration.

All analysis will be carried out with Statistical software SAS v9.4.

REFERENCES

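### Logistic odds ratios for migration over 10 mm are to be presented only for significant factors, so non-significant secondary-objective factors get no odds ratio and modest ones that pass are overstated (minor)

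*Combined protocol and SAP*

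**What the plan says.** Section 3.2 lists density (four categories), approach (lateral, medial, superior), breast thickness and age as secondary objectives. Section 13.2 analyses them against two outcomes.

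- **Migration over 10 mm (yes/no).** A Cochran-Mantel-Haenszel (CMH) test is to be "used to compare differences in categorical variables, e.g. breast density stratified by retracted (arm2) vs nonretracted (arm1"). For age, ANOVA "will be used to compare age differences with controlling of procedures". Then: "Logistic regression analysis will be explored to identify significant factors associated with clip migration". The reporting rule follows: "Odds ratio and two-sided 95% CI will be presented for each factor significantly contributed in the model".
- **Distance in mm.** "ANOVA will be used to evaluate the strength of association (beta coefficient in the regression model"). No reporting filter is attached, but section 13.2 does not say which coefficients or intervals will be given.

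The plan states no significance level, list of terms or selection method for the logistic model.

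**The concern.** The rule makes presentation of a result depend on the result. This has two consequences for the binary outcome.

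1. A factor that is not significant gets no odds ratio and no interval. A reader cannot then separate an odds ratio near 1 with a tight interval from a sizeable one with a wide interval, yet section 3.2 asks whether these factors matter.
2. An odds ratio that is shown has been selected for lying far from 1. If the true effect is modest, the printed value is too large on average, and the nominal 95% interval covers the truth less than 95% of the time.

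At stake is how far the secondary findings on migration over 10 mm can be trusted, for example when density or approach is later cited as a risk factor.

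**Working it through.** **Inputs from the plan.** Section 12.1: 125 per arm, with 50% (Arm 1) and 20% (Arm 2) significant migration. Expected migrations are 62.5 + 25 = 87.5. The plan has no figure for the logistic model. Its Table 1 power, which rests on the same inputs, reproduces closely with a one-sided Fisher's exact test at 5%: 99.96% for 50% v 20% (stated 99.9%) and 93.5% for 50% v 30% (stated 93.1%).

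**Assumptions, because the documents are silent.** Significant means two-sided p < 0.05; the model contains arm and one binary factor; the true odds ratio is 1.2, 1.5 or 2.0; the factor splits 50:50, with 20:80 as a sensitivity case.

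**Step 1: the smallest odds ratio above 1 that can be shown.**
Information = 125 × (0.5 × 0.5 + 0.2 × 0.8) = 51.25.
SE(log OR) = 1/√(51.25 × 0.5 × 0.5) = 0.279.
Threshold = exp(1.96 × 0.279) = 1.73.
By this approximation, no odds ratio between 1 and 1.73 can be presented for a 50:50 factor.

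**Step 2: the filter by normal approximation.** Let z = log(OR)/SE, and let Φ and φ be the standard normal distribution and density functions.
- P(shown) = Φ(z − 1.96) + Φ(−z − 1.96).
- Mean shown log OR = log(OR) + SE × [φ(1.96 − z) − φ(1.96 + z)] / P(shown).
- Coverage when shown = [Φ(1.96) − Φ(1.96 − z)] / P(shown), for z up to 3.92.

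For a true OR of 1.5, z = 0.405/0.279 = 1.451:
- P(shown) = 0.306.
- Mean = exp(0.405 + 0.279 × (0.350 − 0.001)/0.306) = 2.06.
- Coverage = (0.975 − 0.694)/0.306 = 92%.

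**Step 3: simulation.** 20,000 trials per row, logistic model with arm and factor, odds ratio kept if |z| > 1.96. Means are geometric.

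| Split | True OR | Shown in | Mean when shown | Coverage when shown |
|---|---|---|---|---|
| 50:50 | 1.2 | 10% | 1.89 | 71% |
| 50:50 | 1.5 | 30% | 2.12 | 91% |
| 50:50 | 2.0 | 69% | 2.35 | 96% |
| 20:80 | 1.2 | 8% | 2.04 | 62% |
| 20:80 | 1.5 | 22% | 2.39 | 89% |
| 20:80 | 2.0 | 53% | 2.63 | 95% |

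Reporting every estimate from the same trials gives means of 1.19–1.20, 1.50–1.51 and 2.02, with 95% coverage. Repeat runs agree within simulation error. By the Step 2 formula, a true OR of 3.0 at a 50:50 split averages 3.05 when shown, so large effects are hardly distorted.

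**Step 4: what an omitted odds ratio could have said.** Two non-significant factors can carry very different information.
- Age per SD: SE = 1/√51.25 = 0.140. The interval multiplies or divides the odds ratio by exp(1.96 × 0.140) = 1.3.
- A density category holding 10% of patients against one holding 40% (assumed), that is 12.5 v 50 per arm: information = (12.5 × 50/62.5) × (0.25 + 0.16) = 4.1, and SE = 1/√4.1 = 0.494. The factor is exp(1.96 × 0.494) = 2.6.

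If both estimates were 1.0, the intervals would be about 0.76 to 1.31 and 0.38 to 2.63. The first rules out a large effect and the second does not. Under the rule, neither is shown.

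**The case against.** **The factors are analysed elsewhere.** A reader might infer that non-significant factors vanish from the report. The documents do not support that. The CMH test, the ANOVA for age and the distance model cover the same factors with no filter, and the distance model is to give beta coefficients. This stands and narrows the point. It does not remove it: section 13.2 commits to no odds ratio or interval from the CMH test, ANOVA of age compares mean ages, and the betas concern millimetres rather than the 10 mm cut-off that the protocol itself uses.

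**The rule does not say only.** True, but it names which factors are presented, and no other sentence provides for the rest. The plain reading is a filter.

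**The size rests on assumed inputs.** This also stands. Serious coverage loss appears only at a true odds ratio of 1.2, which would be shown in 8–10% of trials. At 1.5 coverage is 89–91%, and at 2.0 it is not reduced. A claim that full reporting of all four factors would almost never occur would depend on assuming that approach has no effect, so it is not made here.

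**By-arm effects.** Section 3.2 speaks of the factors "and their impact on clip migration in both groups (retracted vs nonretracted"), and a reader might infer that the pooled analyses fail this objective. The phrase can equally mean across both groups with arm accounted for, which the arm-stratified CMH test and the arm-controlled ANOVA deliver. It is not part of this point.

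**The model is exploratory.** The plan does say it will be explored, and that keeps the point minor. It is not a reason to filter, because selection does most damage where power was not planned.

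**Conclusion.** The concern holds in a limited form. Followed as written, section 13.2 leaves the binary-outcome odds ratio and interval of any non-significant secondary-objective factor unreported, and overstates modest odds ratios that pass. For a 50:50 factor the overstatement is about 1.6-fold at a true 1.2 (1.89/1.2), 1.4-fold at 1.5 (2.12/1.5) and 1.2-fold at 2.0 (2.35/2.0). Coverage suffers at the first two values but not the third. These sizes depend on the assumed threshold, factor split and true effects; the direction of the bias does not.

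The matter is minor and confined to secondary, exploratory output. The primary Fisher comparison and its power are untouched, and no data are lost.

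**What to change.** Replace the reporting sentence in section 13.2 with:

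> Odds ratios and two-sided 95% CIs will be presented for arm and all four prespecified factors (density, approach, thickness, age) from one model containing all of them, whatever their p-value.

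Add that the distance-model coefficients will be reported with 95% CIs in the same way. The CMH test and the ANOVA can stay as they are.

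Cost: one sentence changed and one added, with no new patients or data. About eight odds ratios are printed (density 3 + approach 2 + thickness 1 + age 1 + arm 1), taking thickness and age as one term each. The downside is that some intervals will be wide, such as the factor of about 2.6 either way for a 10% density category, and the text should describe them as imprecise rather than as evidence of no effect.
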